4.3.5. Removal of Subjects from Therapy or Assessments

A subject may be withdrawn from the clinical study at any time without the subject's consent if the investigator or sponsor determines that it is not in the best interest of the subject to continue participation. In such case, the reason for withdrawal will be documented in the source documents, and the subject will be asked to complete the EOT visit and follow-up visit for safety assessments and pulmonary function.

Study treatment should be discontinued by the investigator (preferably after discussion with the CRO medical monitor, for any of the following conditions:

- Life-threatening AE or a SAE that places the subject at immediate risk
- Serious infections (those requiring parenteral antimicrobial therapy and/or hospitalization)
- Arrhythmia or conduction abnormality, including but not limited to prolonged QT interval corrected for the heart rate using Fridericia's formula (QTcF), where the severity is categorized as Common Terminology Criteria for Adverse Events (CTCAE) Version 5.0 Grade 3 or higher (i.e. QTcF \geq 501 ms or an increase from baseline (Visit 2) in QTcF of $>$ 60 ms) on at least 2 separate ECGs at the same visit
- Increase in liver function tests:
 - AST and/or ALT elevations $>$ 8x ULN: IMP treatment should be withheld and the LFTs should be repeated. IMP should be discontinued if the results are confirmed
 - AST and/or ALT elevations $>$ 3x ULN and $<$ 8xULN: IMP treatment should be withheld. If LFTs do not return to normal within 2 weeks then the IMP should be discontinued. If LFTs return to normal within 2 weeks then IMP could be restarted with close monitoring (e.g. repeat testing twice per week for the first 2 weeks then

weekly for the following month). In the event LFTs become abnormal at any subsequent point during the study (i.e. after rechallenge) then the IMP should be discontinued.

- AST and/or ALT elevations $>3x$ ULN and total bilirubin level (TBL) $>2x$ ULN or international normalized ratio (INR) >1.5 : IMP treatment should be withheld and the LFTs should be repeated. IMP should be discontinued if the results are confirmed.
- AST and/or ALT elevations $>3x$ ULN with the appearance of fatigue, nausea, vomiting, right upper quadrant pain or tenderness, fever, rash and/or eosinophilia ($>5\%$): IMP treatment should be withheld, LFT repeated and IMP discontinued if LFT confirmed or if symptoms and signs persist

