6.5.3. Physical Examination

Physical examinations will be conducted by a physician, trained physician's assistant, or nurse practitioner as acceptable according to local regulation at visits specified in the schedule of activities in Section 6.10 (see also Section 6.1, "Timing of Assessments"). The person conducting the physical examination will document this in the subject's medical records. Clinically significant abnormal findings should be recorded as AEs. At screening the physical examination will include height and weight, and weight should be measured at Visit 9/EOT and Visit 10/EOS.

6.5.4. 12-lead Electrocardiogram

At the time points specified in the schedule of activities Section 6.10 (see also Section 6.1, "Timing of Assessments"), a 12-lead ECG will be recorded and results will be sent for central reading. ECG recordings will be performed before blood/urine sampling and after subjects rested for 5 minutes in supine position. In case an indwelling catheter is used, ECGs may be recorded after blood sampling, provided that there is at least 30 minutes between catheter insertion and the ECG recording. When catheter insertion would fail, the 12-lead ECG needs to be taken before the venipuncture and at least 30 minutes after the failed attempt. Triplicate ECGs will be performed at baseline (Visit 2) only within a time span of 6 minutes, with an approximate 3-minute interval between ECGs. Parameters to be recorded include the following: heart rate, PR interval, QRS interval, uncorrected QT interval, morphology and rhythm analysis (QTcF will be derived during the statistical analysis). ECG parameter normal ranges are presented in Appendix 4. QTcF will be considered as normal if ≤ 450 ms (male) and ≤ 460 ms (female), while subjects experiencing a prolongation of QTcF to ≥ 501 ms or an increase from baseline >60 ms should be discontinued from IMP (see Section 4.3.5). Immediately after recording, the ECGs will be reviewed by the investigator on clinical significant abnormalities. This immediate review during the visit needs to be documented in the subject's source. After receipt of the central report, also all flagged ECG abnormalities need to be assessed by the investigator on clinical relevance. All clinically significant abnormal ECG values should be recorded as AEs.

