Appendix 4 Normal Ranges

NORMAL RANGES FOR VITAL SIGNS

Normal ranges applicable in supine position (after 5 minutes):

Systolic blood pressure (mmHg)	Diastolic blood pressure (mmHg)	Heart rate (bpm)	Oral/Tympanic temperature (°C)	Respiratory rate (RR) (breaths/minute)
$90 \leq \text{SBP} \leq 150$	$45 \leq \text{DBP} \leq 90$	$50 \leq \text{HR} \leq 100$	$35.5 \leq t^{\circ} \leq 37.5$	$12 \leq \text{RR} \leq 18$

NORMAL RANGES FOR ECG PARAMETERS

Normal ranges applicable in supine position (after 5 minutes):

PR (ms)	QRS (ms)	QTcF (ms)	Heart rate (bpm)
$120 \leq \text{PR} \leq 220$	$\text{QRS} \leq 120$	QTcF ≤ 450 (male) QTcF ≤ 460 (female)	$50 \leq \text{HR} \leq 100$

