5.3.3. Electrocardiogram

5.3.3.1. Available Data

The following electrocardiogram (ECG) parameters will be analyzed: PR interval, heart rate (HR), RR interval, QRS duration, QT interval, and QTcF interval.

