5.3.3.3. Abnormalities

The actual analysis values and changes from baseline of the QT and QTcF parameters will be categorized into the abnormality classes as defined in ICH-E14 The Clinical Evaluation of QT/QTc Interval Prolongation and Proarrhythmic Potential for Non-Antiarrhythmic Drugs (Step 4 Version). For PR and HR the categorization as specified in the protocol is used.

Table 7 Abnormalities on ECG Parameters

Parameter	Abnormality	Limits
Abnormalities on actual values		
QT and QTcF (ms)	QT ≤ 450 450 < QT ≤ 480 480 < QT ≤ 500 QT > 500	≤ 450 450 < value ≤ 480 480 < value ≤ 500 > 500
PR (ms)	L N H	< 120 120 ≤ value ≤ 220 > 220
HR (bpm)	L N H	< 50 50 ≤ value ≤ 100 > 100
Abnormalities on change from baseline		

QT and QTcF (ms)	QT change \leq 30	\leq 30
	30 < QT change \leq 60	30 < change \leq 60
	QT change > 60	> 60

Worst-Case Abnormality

The worst-case post-baseline categorized actual analysis value and the worst-case categorized change from baseline will be determined per subject, per parameter, and for each analysis period, using all non-missing post-baseline records (including unscheduled and follow-up visits).

For QT and QTcF, the worst-case categorized actual analysis value is the category corresponding to the highest post-baseline actual value. The worst-case change from baseline is the category corresponding to the largest increase (positive change) from baseline.

For PR and HR, the worst-case post-baseline abnormality L, N or H is determined as follows:

- L = low: at least one post-baseline result is classified as L.
- N = normal: all post-baseline results are classified as N.
- H = high: at least one post-baseline result is classified as H.

If, for a subject, both L and H are reported, the subject will be counted twice in a table: once with a worst-case L and once with a worst-case H.

Treatment-Emergent Abnormalities

For QT and QTcF, an abnormal post-baseline category for actual values is defined as treatment-emergent when the abnormality is worse compared to the abnormality at baseline. When the baseline value is missing, post-baseline abnormalities are considered as treatment-emergent. An abnormal category for change from baseline is always treatment-emergent.

For PR and HR, post-baseline abnormalities L or H are defined as treatment-emergent when they differ from the abnormality class of the baseline result. When the baseline result is missing, post-baseline abnormalities L or H are considered as treatment-emergent.

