5.3.3.4. Presentation of Results

No formal inferential statistics (p-values) will be derived.

Continuous parameters will be summarized by means of descriptive statistics (including 95% CI of the mean change) by parameter, treatment group, and analysis window. Actual values and changes from baseline will be tabulated separately.

Boxplots of the actual values over time and of the mean (+/- SE) change from baseline will be prepared for all parameters.

The analysis of abnormalities will focus on assessments reported during the treatment period. Results reported during the screening or follow-up period will only be listed.

Abnormalities of the actual values will be presented as shift tables of the worst-case abnormality versus the baseline abnormality. The table will be created per parameter (QT, QTcF, PR and HR) and treatment group.

A frequency table of the number (percent) of subjects with treatment-emergent worst-case abnormalities (QT, QTcF, PR and HR) and the worst change (QT and QTcF) per parameter and treatment group will be presented.

A frequency table per treatment group and time point of the ECG interpretation findings as transferred from the central reader may be provided.

A listing per treatment group, per subject, and per time point of all post-baseline time points scored as out-of-normal-range, plus also the baseline reference time point will be provided.

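### The SAP gives QRS duration no abnormality class and leaves it out of the ECG shift and treatment-emergent tables, although the protocol sets a normal limit for it

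*SAP*

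**What the plan says.** Protocol 6.5.4 includes QRS among the ECG measurements: "Parameters to be recorded include the following: heart rate, PR interval, QRS interval, uncorrected QT interval, morphology and rhythm analysis". It then states that "ECG parameter normal ranges are presented in Appendix 4". The part of Appendix 4 titled "NORMAL RANGES FOR ECG PARAMETERS" covers PR (120 to 220 ms), QRS (at most 120 ms), QTcF (at most 450 ms in men and 460 ms in women) and heart rate (50 to 100 bpm).

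SAP 5.3.3.1 takes QRS into the analysis: "The following electrocardiogram (ECG) parameters will be analyzed: PR interval, heart rate (HR), RR interval, QRS duration, QT interval, and QTcF interval".

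SAP 5.3.3.3 and its Table 7 then define the abnormality classes. QT and QTcF take ICH-E14 classes. For the rest the rule is "For PR and HR the categorization as specified in the protocol is used". QRS has no row in the table. The worst-case and treatment-emergent rules in the same section are written for QT, QTcF, PR and HR.

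SAP 5.3.3.4 keeps to that list. For the shift tables it says "The table will be created per parameter (QT, QTcF, PR and HR) and treatment group", and the treatment-emergent frequency table names the same four parameters. The listing of out-of-range time points names no parameters and no source of ranges.

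**The concern.** The protocol sets one table of ECG normal ranges. The SAP adopts that table for PR and HR, replaces it with a recognised classification for QTcF, and is silent on QRS. Vital signs are treated differently: SAP 5.3.4.2 scores them against Appendix 4 without singling out any parameter. The readable text gives no reason for leaving QRS out.

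At stake is a simple safety count. The protocol treats conduction as worth watching: clinically significant conduction abnormality is an exclusion ground (Protocol 4.3.3, criterion 5.1), and conduction abnormality of CTCAE Grade 3 or higher is a ground for stopping study drug (Protocol 4.3.5). A reader of the ECG tables would expect to see how many subjects in each arm developed a QRS above the protocol's limit, as they will for PR. The interim package in SAP 4.2 includes ECG abnormality tables and refers to Section 5 for details, so it would carry the same gap.

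**Working it through.** There is no stated figure to reproduce, so the check compares the lists.

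| ECG parameter | Range in Protocol Appendix 4 | Analysed (SAP 5.3.3.1) | Class in SAP Table 7 | In shift and frequency tables (SAP 5.3.3.4) |
|---|---|---|---|---|
| PR | 120 to 220 ms | yes | L/N/H, protocol range | yes |
| HR | 50 to 100 bpm | yes | L/N/H, protocol range | yes |
| QTcF | ≤450 ms (men), ≤460 ms (women) | yes | ICH-E14 classes | yes |
| QRS | ≤120 ms | yes | none | no |
| QT | none | yes | ICH-E14 classes | yes |
| RR | none | yes | none | no |

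Parameters with a protocol range, {PR, QRS, QTcF, HR}, minus parameters the SAP scores, {QT, QTcF, PR, HR}, leaves {QRS}.

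**Applying the rules to two subjects**
- PR from 200 to 230 ms: the baseline is N (120 ≤ 200 ≤ 220) and the later value is H (230 > 220). The class differs from baseline, so this is a treatment-emergent High and is counted in both tables.
- QRS from 100 to 145 ms: the value passes 120 ms, but no class exists at either time. No worst-case class or treatment-emergent flag can be derived, and the subject is counted in neither table.

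**What the remaining output shows**

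Under SAP 3.5.2 and 5.3.3.4, QRS will have a mean, SD, median, minimum and maximum by arm and analysis window, separately for actual values and changes. The following example is hypothetical and predicts nothing. Take the planned GLPG1205 arm of 60 × 2/3 = 40 subjects. Suppose some of them go from 100 to 145 ms in the same window and the rest do not change.

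| Subjects widening | Shift in arm mean | Maximum value | Maximum change | Count a scored table would give |
|---|---|---|---|---|
| 1 of 40 | 45/40 = 1.1 ms | at least 145 ms | at least +45 ms | 1 (2.5%) |
| 3 of 40 | 3 × 45/40 = 3.4 ms | at least 145 ms | at least +45 ms | 3 (7.5%) |

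The maxima reveal that widening happened, but they are the same in both rows, so they do not give the number of subjects. Nor does a maximum value show whether that subject was already above 120 ms at baseline, or a maximum change show whether the limit was crossed. A completer has five scheduled post-baseline ECGs (Visits 3, 6, 8, 9 and 10). Summaries by window cannot be combined into a per-subject worst case.

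**The case against.** The strongest reply is that this is a consistent scope choice. The same four parameters appear in Table 7, in both derivation rules and in both tables. RR is also analysed without classes. Protocol 7.3.5 asks only that safety data be listed and/or summarised, and does not require ECGs to be scored against Appendix 4. QRS extremes will be in the descriptive tables and boxplots. Under Protocol 6.5.4 the investigator reviews each ECG, assesses abnormalities flagged by the central reader, and records clinically significant ones as adverse events, which are then tabulated. A frequency table of central-reader findings is optional in SAP 5.3.3.4. All of this is accurate, and it keeps the point small. It does not supply the missing count. RR is not a parallel, because Appendix 4 gives it no range.

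A reader might infer more, and the documents do not support it:

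- **That a high QRS appears in no listing.** The listing sentence names no parameters. The QT and QTcF rows of Table 7 are not the protocol's normal ranges, so out-of-range may well mean Appendix 4, which includes QRS. The SAP's Introduction also puts derivation details and mock listings in a separate document. The text is unclear; it does not exclude QRS.
- **That QRS widening would be hidden, or that the tables could show no conduction signal.** Maxima, boxplots and adverse events remain, and PR, which also measures conduction, is fully categorised.
- **That the gap affects decisions to stop treatment.** Protocol 4.3.5 refers to CTCAE grade, gives figures for QTcF only and sets no QRS limit. Investigators apply it during the trial, independently of these tables.

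**Conclusion.** The point holds as a gap in descriptive safety reporting. QRS is the only ECG parameter with a protocol normal range that the SAP analyses but never classifies. As a result, no planned shift or treatment-emergent table counts subjects who newly exceed 120 ms, and the rule for the listing is ambiguous. Analysts would follow the stated parameter list, so the gap is unlikely to be filled in programming.

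The size is modest. No data are lost, no test or efficacy result changes, and the trial is exploratory with about 60 subjects. The documents give no basis for expecting any particular number of QRS abnormalities, so the practical effect cannot be estimated. The conclusion assumes that the mock outputs follow the SAP text. Parts of SAP 5.5 are redacted, so a reason stated there cannot be excluded.

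**What to change.** 1. Add a QRS row to Table 7 using the existing Appendix 4 limit: N for 120 ms or less, H for more than 120 ms.
2. Add QRS to the sentence that adopts the protocol categories for PR and HR, and to the PR/HR parts of the worst-case and treatment-emergent rules in SAP 5.3.3.3.
3. Add QRS to the parameter lists for the shift table and the frequency table in SAP 5.3.3.4.
4. State that the Appendix 4 ranges drive the out-of-range listing. Uncorrected QT has no such range, so also say whether its Table 7 class triggers listing.

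If QRS is left out on purpose, give the reason in the SAP instead.

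The data are already collected and the ECGs are centrally read, so the cost is about one more row per output. A single cut-off has limits: 119 to 121 ms would count as treatment-emergent, while 125 to 160 ms would not, because the class is unchanged. The second case can occur because eligibility sets no numeric QRS limit. The new count should therefore be read together with the change-from-baseline summary already planned.

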5.3.3.4. Presentation of Results

No formal inferential statistics (p-values) will be derived.

Continuous parameters will be summarized by means of descriptive statistics (including 95% CI of the mean change) by parameter, treatment group, and analysis window. Actual values and changes from baseline will be tabulated separately.

Boxplots of the actual values over time and of the mean (+/- SE) change from baseline will be prepared for all parameters.

The analysis of abnormalities will focus on assessments reported during the treatment period. Results reported during the screening or follow-up period will only be listed.

Abnormalities of the actual values will be presented as shift tables of the worst-case abnormality versus the baseline abnormality. The table will be created per parameter (QT, QTcF, PR and HR) and treatment group.

A frequency table of the number (percent) of subjects with treatment-emergent worst-case abnormalities (QT, QTcF, PR and HR) and the worst change (QT and QTcF) per parameter and treatment group will be presented.

A frequency table per treatment group and time point of the ECG interpretation findings as transferred from the central reader may be provided.

A listing per treatment group, per subject, and per time point of all post-baseline time points scored as out-of-normal-range, plus also the baseline reference time point will be provided.

5.3.4. Vital Signs

5.3.4.1. Available Data

The following vital signs parameters will be analyzed: heart rate, respiratory rate, diastolic and systolic blood pressure, oral or tympanic body temperature. If blood pressure is collected standing and supine, then results are presented by assessment position.

5.3.4.2. Abnormalities

Vital signs data will be evaluated for abnormalities based on the normal ranges as defined in Appendix 4 of the CSP.

Values equal to the boundaries are still considered normal (N). A value is classified as abnormally low (L) when the value < lower limit of the normal range. A value is classified as abnormally high (H) when the value > upper limit of the normal range.

5.3.4.3. Treatment-Emergent Principle

A post-baseline abnormality class L or H is defined as treatment-emergent when it differs from the abnormality class at baseline. If the baseline result is missing, a post-baseline abnormality L or H will be considered as treatment-emergent.

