Appendix 3 Contraindications for 6-Minute Walk Test

Absolute contraindications:

- Unstable angina during the previous month [27]
- Myocardial infarction during the previous month [27]
- Oxygen saturation measured by pulse oximetry <88 % after 10 minutes of rest of breathing room air or at baseline oxygen flow rate [30].

Relative contraindications [27]

- Resting heart rate >120 beats per minute
- SBP >180 mmHg
- DBP >100 mmHg

Source: [27]

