5.3.2.4. Definition of Non-Graded Abnormalities

For laboratory tests provided by the laboratory, the position of the actual analysis values versus their normal ranges will be determined directly by using the position indicator provided in the database as reported by the central laboratory, expressing the classes for these analysis values as low (L), normal (N) or high (H). L, N, and H are further referred to as non-graded abnormalities.

Only for tests for which no toxicity gradings are specified in Section 5.3.2.3, analysis of the classification according to normal ranges will be done.

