5.3.2.6. Treatment-Emergent Principle

Toxicity Grades

A post-baseline toxicity grade 1, 2, 3 or 4 is defined as treatment-emergent when higher than the toxicity grade of the baseline result. If the baseline result is missing, a post-baseline toxicity grade 1, 2, 3 or 4 will be considered as treatment-emergent.

Non-graded Abnormalities

A post-baseline non-graded abnormality class L or H is defined as treatment-emergent when it differs from the abnormality class of the baseline result. If the baseline result is missing, a post-baseline abnormality L or H will be considered as treatment-emergent.

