5.3.4.5. Presentation of Results

No formal inferential statistics (p-values) will be derived.

Continuous parameters will be summarized by means of descriptive statistics (including 95% CI of the mean change) by parameter (and position if applicable), treatment group, and analysis window. Actual values and changes from baseline will be tabulated separately.

Boxplots of the actual values over time and of the mean (+- SE) change from baseline will be prepared for all parameters.

The analysis of abnormalities will focus on assessments reported during the treatment period. Results reported during the screening or follow-up period will only be listed.

Abnormalities of the actual values will be presented as shift tables of the worst-case abnormality versus the baseline abnormality. The table will be created per parameter (and position if applicable) and treatment group.

A frequency table of the number (percent) of subjects with treatment-emergent worst-case abnormalities per parameter and treatment group will be presented.

A listing per treatment group, per subject, and per time point of all post-baseline time points scored as treatment-emergent and out-of-normal-range, plus also the baseline reference time point will be provided.

The vital signs measurements collected at the start and finish of the 6MWT will be listed separately.

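### Vital signs and ungraded laboratory tests: worsening within the same abnormal class is left out of the treatment-emergent tables and the abnormality listings

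*SAP*

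**What the plan says.** **Vital signs.** SAP 5.3.4.2 classes each value against the ranges in Protocol Appendix 4 (for example systolic pressure 90 to 150 mmHg, heart rate 50 to 100 bpm): "A value is classified as abnormally low (L) when the value < lower limit of the normal range", with the mirror rule for high. There are no further levels. SAP 5.3.4.3 then states: "A post-baseline abnormality class L or H is defined as treatment-emergent when it differs from the abnormality class at baseline". The one exception is "If the baseline result is missing, a post-baseline abnormality L or H will be considered as treatment-emergent". SAP 5.3.4.5 plans a frequency table of treatment-emergent worst cases, a shift table of worst case against baseline class, continuous summaries, and a listing "of all post-baseline time points scored as treatment-emergent and out-of-normal-range", with the baseline value beside them.

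**Laboratory tests without grades.** SAP 5.3.2.4 limits low/normal/high classing to these tests: "Only for tests for which no toxicity gradings are specified in Section 5.3.2.3, analysis of the classification according to normal ranges will be done". SAP 5.3.2.6 gives the same class-change rule: "A post-baseline non-graded abnormality class L or H is defined as treatment-emergent when it differs from the abnormality class of the baseline result". The listing in 5.3.2.8 carries the same double condition as the vital-sign listing.

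**ECG.** The corresponding listing in SAP 5.3.3.4 is "of all post-baseline time points scored as out-of-normal-range", with no treatment-emergent condition.

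**The concern.** With one abnormal level per direction, a rule that asks for a change of class cannot register further movement in the same direction. A subject already above a limit at baseline can rise by any amount and still not be treatment-emergent on the high side. The listing is the output that would let a reader find that subject, and it is filtered by the same rule.

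Two things are at stake. First, the frequency table can rank subjects the wrong way round for safety, counting a trivial crossing of a limit and omitting a large deterioration beyond it. Second, the affected tests include some of direct interest. Protocol 2.2.4 reports that two subjects on 200 mg had clinically significant high hematocrit, hemoglobin and red cell count. Hemoglobin is graded in SAP Appendix I; hematocrit and red cell count appear in neither Table 5 nor Table 8. Lactate dehydrogenase and brain natriuretic peptide are also collected (Protocol 6.5.2) and ungraded.

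**Working it through.** The plan states no figure on this point, so there is none to reproduce. The check applies the written rules to example values.

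**Step 1: the rules as formulas.** Limits come from Protocol Appendix 4, classes from SAP 5.3.4.2, and the rule from 5.3.4.3.
- Class = L if value < lower limit, H if value > upper limit, otherwise N.
- Treatment-emergent (TE) = post-baseline class is L or H, and either baseline is missing or the post-baseline class differs from the baseline class.
- Listed in 5.3.4.5 = TE and out of range. Class L or H already means out of range, so for vital signs the listing is exactly the TE set.

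**Step 2: hypothetical pairs.**

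| Parameter | Baseline | Post-baseline | Class | Change | TE and listed? |
|---|---|---|---|---|---|
| SBP | 148 | 152 | N to H | +4 | Yes |
| SBP | 155 | 195 | H to H | +40 | No |
| SBP | 151 | 210 | H to H | +59 | No |
| HR | 105 | 150 | H to H | +45 | No |
| HR | 49 | 35 | L to L | -14 | No |
| HR | 105 | 45 | H to L | -60 | Yes |
| SBP | missing | 155 | missing to H | n/a | Yes |

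Same-direction worsening is never captured when a baseline value exists. A move to the opposite abnormal class, or a missing baseline, is captured.

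**Step 3: what the other planned outputs show for 151 to 210.**
- Shift table: one subject in the H-to-H cell, the same as a subject going from 151 to 151.
- Change-from-baseline statistics: SAP 3.5.2 includes minimum and maximum, so +59 can show as the maximum for its arm and window. Under SAP 3.3.3 this happens only if it is the value closest to the target day. No subject is identified.
- Box plots of actual values: the same limits apply.
- Percentages: by SAP 3.5.3 the subject stays in the denominator, but cannot enter the numerator for high values.

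**Step 4: how the SAP treats worsening elsewhere.**

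| Data | Does worsening from an abnormal baseline count? | Listing filtered to TE? |
|---|---|---|
| Adverse events (5.3.1.1) | Yes, worsening of an existing event is TE | n/a |
| Graded laboratory tests (5.3.2.6, 5.3.2.8) | Yes, if the grade is higher than at baseline | Yes |
| QT/QTcF (5.3.3.3, 5.3.3.4) | Yes, if the category is worse; change categories are added | No |
| ECG PR and HR (5.3.3.3, 5.3.3.4) | No, class change only | No |
| Vital signs (5.3.4.3, 5.3.4.5) | No | Yes |
| Ungraded laboratory tests (5.3.2.6, 5.3.2.8) | No | Yes |

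Only the last two rows combine a rule that ignores same-class worsening with a listing that hides it. Heart rate shows the inconsistency most plainly. With the same 50 to 100 limits, a rise from 105 to 150 is listed as an ECG value and omitted as a vital sign. Vital signs are scheduled at every visit, whereas the schedule has no ECG at Weeks 4, 8 and 16.

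**The case against.** The strongest reply is that little is really lost. Changes from baseline are summarised by arm with extremes, shift tables count every H-to-H subject, and clinically significant vital signs and laboratory values are to be recorded as adverse events (Protocol 6.5.5, 6.5.2, 9.1.5) and so are listed. Heart rate is also captured by ECG. The red-cell signal has a graded route through hemoglobin, and the trial dose is 100 mg, for which Protocol 2.3.1 reports no clinically relevant laboratory abnormalities. Safety is descriptive, the study is a small proof of concept, and an independent committee reviews unblinded safety data.

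Much of this stands, and it rules out several stronger readings that a reader might infer:
- *That such worsening is invisible, or in no subject-level output.* The summaries and the adverse event route contradict this. SAP 3.3.3 also says that values not selected for a window are listed, SAP 5.3.2.8 and 5.3.4.5 list screening and follow-up results, and SAP section 1 places the mock listings in a separate document not available here.
- *That the ECG section is better throughout.* PR and heart rate use the same class-change rule; their advantage is the unfiltered listing.
- *That a stated share of subjects is affected, or that the respiratory rate limit of 18 is low for this population.* The documents give no baseline distribution and no basis for either statement.
- *That Protocol Appendix 3 supplies a ready second severity level.* Limits such as "Resting heart rate >120 beats per minute" are relative contraindications to the walk test and cover the high side only.

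What the reply does not answer is narrower. Group summaries identify no subject and do not count those who worsened, and the adverse event route depends on the investigator's judgement of significance. No reason is given for filtering these two listings when the ECG listing is not filtered.

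**Conclusion.** The point holds in a limited form. When a baseline value exists, H-to-H or L-to-L worsening in vital signs and ungraded laboratory tests is excluded from the treatment-emergent frequency tables and the abnormality listings, and the shift table does not show its size. Apart from the incidental listings noted under the objection, what remains is group-level continuous summaries or an investigator-reported adverse event. This departs from the SAP's own handling of adverse events, graded laboratory tests and QT/QTcF, and from its ECG listing.

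The size cannot be put as a percentage. Those affected are the subjects already out of range at baseline who move further out, and the documents do not say how many to expect. The conclusion assumes that the listing sentences will be programmed as written. It has no bearing on the efficacy analyses. It is a cheap improvement to safety reporting, not a flaw that undermines the safety evaluation.

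**What to change.** In SAP 5.3.2.8 and 5.3.4.5, delete *treatment-emergent and* from the listing sentence. All post-baseline out-of-range values are then listed with the baseline value, as 5.3.3.4 already does for ECG. Add a flag for values that are treatment-emergent, so that the filtered view can still be recovered.

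Optionally, tabulate by arm the worst change from baseline among subjects already out of range at baseline, for vital signs and ungraded laboratory tests. This should be description only: with about 20 placebo subjects planned, the cells may be very small.

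The cost is a wording change in two sentences and slightly longer listings for about 60 subjects. No new data are needed, and the treatment-emergent definition and frequency tables can stay as they are.
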